2.8. Medical History

Medical history terms will be coded using the Medical Dictionary for Drug Regulatory Affairs (MedDRA) version 18.1. A summary table by body system and preferred term will be presented. The complete medical history information will also be presented in a data listing.

2.9. Safety Evaluations

2.9.1. Adverse Events

Adverse events will be coded using the Medical Dictionary for Drug Regulatory Affairs (MedDRA) version 18.1 and tabulated, including categorical information of interest such as onset and resolution times, time of onset relative to dose, severity at onset, maximum severity, causal relationship to study medication, and action taken.

Treatment-emergent adverse events (TEAEs) are defined as any AE that started after the first dose of study medication or started prior to the first dose but increased in severity or frequency after dosing. The incidence of TEAEs will be presented by system organ class and preferred term. Adverse events will also be summarized by severity and relationship to the study drug.

The incidence of serious AEs, drug-related AEs, serious and drug-related AEs, and any AEs resulting in discontinuation from the study will be listed. Adverse events will be presented in decreasing order of frequency (preferred term only) to better assess the most frequent adverse events.

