Approximately 24 weeks after randomization, subjects will report to the clinic following a minimum 10-hour fast for a follow-up visit (Visit 5) to provide a blood sample for plasma concentration, chemistry (GGT, ALT, AST, and total bilirubin), bone turnover markers, fasting lipid profile, and coagulation. Concomitant medications and adverse events will be reviewed. They will have a physical examination, including weight, and vital signs will be measured. They will provide data for the Grip Strength, and SPPB. Post-fracture PADLs/IADLs and SF-36 will

be conducted by subject interview. Following the interviews, they will perform the 6MWT and BORG Scale. ECG and DXA scans will be performed. Subjects will exit the study.

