7.8 Visit 5 Follow- Up (Day 168±5)

At Visit 5, the following will take place:

- Record concomitant medications
- Physical examination, including weight
- Vital signs (SBP, DBP, HR)
- Plasma concentration sample collection
- GGT, ALT, AST, and total bilirubin
- Bone Turnover Markers
- Fasting Lipid Profile
- Coagulation
- 12-lead ECG
- DXA Scan
- Grip Strength and SPPB (to be performed before the PADLs/IADLs and SF-36)
- Post-fracture PADLs/IADLs
- SF-36
- 6MWT and BORG Scale (to be performed after the PADLs/IADLs and SF-36)
- Record adverse events

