10.4.2 Serious Adverse Events

The Sponsor will adhere to all SAE FDA regulatory reporting requirements as per 21 CFR 312.32.

The Principal Investigator or other study personnel must immediately (within 24 hours of becoming aware of the event) inform the Sponsor or their designated representative (CRO) of any AE considered serious or otherwise medically significant (i.e. SAEs). This notification of SAEs can be via facsimile or email transmission of a written SAE reporting form (SAERF) signed by the Principal Investigator. To the best of the Investigator's ability, the supplied SAERF must be completed in its entirety or at a minimum must include the subject's demographics, relevant medical history, the diagnosis and description of the SAE, concomitant medications, and the Principal Investigator's assessment as to whether the SAE was or was not related to the use of the study medication. The initial SAERF and any subsequent follow-up SAERFs submitted to provide more accurate, corrected or new information must be signed by the Investigator. The Investigator and Site Personnel must make every reasonable effort to obtain, from other institutions if necessary, all supporting medical case records as needed to comply with expedited investigational new drug (IND) safety reporting.

If the SAE involves expedited IND safety reporting (as determined by the Sponsor or designee), all supporting medical records must be submitted to the Sponsor or designee within 4 calendar days for death or life threatening events, and 10 calendar days for all other events. In cases where medical records and supporting documentation are unobtainable, the Investigator must generate a narrative of the event utilizing, when necessary, interviews with the subject, their family members and care givers as appropriate. The Principal Investigator must also promptly inform the governing IRB of the SAE in accordance with the governing IRB's requirements. The DMC will be notified by the Sponsor or Sponsor's authorized designee. Ultimately, the final SAE diagnosis recorded on the final serious adverse event reporting form (SAERF) must reconcile with the subject's AE log in the study's database.

Any SAE that occurred within 30 days after the final visit will be followed and reported as above.

The CRO contact information for SAERF and supporting medical records submission is as follows:

[name]
Safety Office, Integrium, LLC
Office: [contact]
Cellular: [contact]
[contact]
Email: [contact]

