1.2. Study Overview

This is a phase II, randomized, double-blind, parallel group, placebo-controlled, multi-center study to investigate the safety, tolerability, and efficacy of VK5211 after 12 weeks of treatment.

Males and females \geq 65 years old who are ambulatory and recovering from a hip fracture will be eligible for participation 3-11 weeks post-injury.

After completing all Screening requirements, subjects will be randomized to one of four treatment arms (VK5211 0.5 mg, 1.0 mg, 2.0 mg, or placebo) in a 1:1:1:1 ratio and will receive their first dose of study treatment in the clinic.

The first bottle of study treatment will be dispensed and subjects will be instructed to take one oral dose of the assigned treatment at approximately the same time every morning, 30 minutes prior to breakfast.

Subjects will undergo safety and efficacy assessments as specified in the protocol on an approximately 4-week basis for a total treatment period of approximately 12 weeks. Following the 12-week treatment period, subjects will be followed for an additional 12-week period for assessment of safety and duration of drug effect.

During the study safety will be assessed on an ongoing basis by adverse events, identification of dose-limiting toxicities (DLTs) (if any), plasma concentrations, general physical examinations, vital signs, clinical laboratory assessments in blood, urine, as well as other specialized testing as required.

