1.3.2. Secondary Objectives

The secondary objectives of this study are:

- To assess the safety and tolerability of VK5211 after 12 weeks of treatment by comparing overall adverse events, vital signs, 12-lead ECG data, physical examinations, and hematology/chemistry/urinalysis data to placebo.
- To determine the efficacy of VK5211 after 12 weeks of treatment by mean placebo-corrected change in:
 - Hip bone mineral density (BMD) assessed by DXA
 - Total lean body mass (TLBM)
 - Appendicular lean body mass (ALBM)
 - Bone turnover markers (s-CTX and s-PINP)
- To assess plasma concentration of VK5211 near T_{max} and at trough levels in relation to total lean body mass.

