14.2.18.2.3	Summary of Whole Body Dual Energy X-Ray Absorptiometry (DXA) scan – Appendicular Lean Body Mass – Site Results with DXA Type Correction Factor – Sex Effect - Stringent Definition of Valid DXA - Per Protocol Population
14.2.18.2.4	Summary of Whole Body Dual Energy X-Ray Absorptiometry (DXA) scan – Appendicular Lean Body Mass – Site Results with DXA Type Correction Factor - Liberal Definition of Valid DXA - Per Protocol Population

Table Number	Table Title
14.2.18.2.5	Summary of Whole Body Dual Energy X-Ray Absorptiometry (DXA) scan – Appendicular Lean Body Mass – Site Results with DXA Type Correction Factor – Multiple Imputation Method - Liberal Definition of Valid DXA - Per Protocol Population
14.2.18.2.6	Summary of Whole Body Dual Energy X-Ray Absorptiometry (DXA) scan – Appendicular Lean Body Mass – Site Results with DXA Type Correction Factor – Sex Effect - Liberal Definition of Valid DXA - Per Protocol Population
14.3.1.1.1	Summary of Adverse Events – Safety Population
14.3.1.1.2	Summary of Treatment Emergent Adverse Events by System Organ Class and Preferred Term – Safety Population
14.3.1.1.3	Summary of Treatment Emergent Adverse Events in Decreasing Order of Frequency by Preferred Term – Safety Population
14.3.1.1.4	Summary of Treatment Emergent Adverse Events by Severity – Safety Population
14.3.2.1	Summary of Treatment Emergent Adverse Events Leading to Discontinuation by System Organ Class and Preferred Term – Safety Population
14.3.2.2.1	Summary of Serious Adverse Events by System Organ Class and Preferred Term – Safety Population
14.3.2.2.2	Summary of Serious Adverse Events in Decreasing Order of Frequency by Preferred Term – Safety Population
14.3.3.1	Summary of Liver Function Tests – Safety Population
14.3.3.2	Summary of Safety Lab Parameters – Hematology – Safety Population
14.3.3.3	Summary of Safety Lab Parameters – Chemistry – Safety Population
14.3.3.4	Summary of Safety Lab Parameters – Urinalysis – Safety Population
14.3.4.1	Shifts in Liver Function Tests – Safety Population
14.3.4.2	Shifts in Selected Lab Parameters by CTC Grade – Safety Population
14.3.4.3	Shifts in Safety Lab Parameters – Hematology – Safety Population
14.3.4.4	Shifts in Safety Lab Parameters – Chemistry – Safety Population
14.3.5	Summary of Vital Signs – Safety Population
14.3.6	Summary of Electrocardiogram Results – Safety Population
14.3.7	Summary of Physical Exam Findings – Safety Population

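### The treatment-emergent AE definition has no end and no on-drug/off-drug split is specified, so about half of a completer's TEAE window falls after dosing stops

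*SAP*

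**What the plan says.** SAP 2.9.1 and Protocol 9.5.1 use the same definition: "Treatment-emergent adverse events (TEAEs) are defined as any AE that started after the first dose of study medication", or that began earlier and worsened after dosing. Neither gives an end date or a lag after the last dose.

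The study has two equal periods. SAP 1.2 states: "Following the 12-week treatment period, subjects will be followed for an additional 12-week period for assessment of safety and duration of drug effect". The last planned dose is at Visit 4 (Day 84). The activity list for Visit 5 (Protocol 7.8, Day 168±5) includes "Record adverse events". Protocol 10.4.2 extends collection of serious events: "Any SAE that occurred within 30 days after the final visit will be followed and reported as above".

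The safety objective in SAP 1.3.2 is tied to the treatment period: "To assess the safety and tolerability of VK5211 after 12 weeks of treatment by comparing overall adverse events", among other safety data, with placebo.

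SAP 4.1 lists four TEAE tables: 14.3.1.1.2 ("Summary of Treatment Emergent Adverse Events by System Organ Class and Preferred Term – Safety Population"), 14.3.1.1.3 (by frequency), 14.3.1.1.4 (by severity) and 14.3.2.1 (leading to discontinuation). Tables 14.3.1.1.1, 14.3.2.2.1 and 14.3.2.2.2 cover AEs overall and SAEs. None of these titles names a study period. SAP 2.9.1 does promise to tabulate onset time relative to dose, but no title carries it. AEs are not among the variables of the Month 3 primary analysis (SAP 2.11), so the AE tables come with the final analysis, after follow-up is complete.

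**The concern.** The objective asks how VK5211 compares with placebo over 12 weeks of treatment. A table built on the open-ended definition answers a different question: how the arms compare over 24 weeks, half of them untreated.

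The Protocol introduction describes this population as having high morbidity, mortality, refracture and rehospitalization, so events unrelated to drug can be expected during follow-up. If they occur at similar rates in all arms, adding them brings the arms' percentages closer in relative terms. With 104 randomized (26 per arm), readers will judge safety by eye from these percentages. Reversible on-drug effects are the kind most easily blurred. In the elderly Phase I study, for example, a subject with ALT at 7 times the upper limit of normal was down to 62 U/L about two weeks later. An event that begins on withdrawal would also be counted, but could not be told apart from an on-drug event in the summary.

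**Working it through.** The plan gives no figure for the AE comparison, so there is none to reproduce. AE rates and on-drug effects below are assumptions.

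**1. Share of the window off drug**
- Planned days: dosing to Day 84, AE recording to Day 168. Off-drug share = (168 − 84)/168 = 50%.
- Visit windows (Visit 4 at Day 79 to 86, Visit 5 at Day 163 to 173): from (163 − 86)/163 = 47% to (173 − 79)/173 = 54%.
- SAEs with the 30-day tail: (84 + 30)/(168 + 30) = 114/198 = 58%.

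**2. Rate ratio**

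Assume a constant background rate and a true on-drug rate ratio R that persists for L days after the last dose and then returns to 1. The whole-study rate ratio is [R(84 + L) + (84 − L)]/168.
- R = 2, L = 0: 252/168 = 1.50.
- R = 3, L = 0: 336/168 = 2.00.
- L = 35: the Phase I hormone changes had reversed by Day 56 of a 21-day study (Protocol 5.3), and 56 − 21 = 35. R = 2 gives 287/168 = 1.71; R = 3 gives 406/168 = 2.42.
- L = 84: no dilution.

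**3. Risks**

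Let p be the on-drug 12-week risk and b the off-drug 12-week risk, equal in all arms. The 24-week risk is 1 − (1 − p)(1 − b), so the risk difference is multiplied by (1 − b).

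| On drug, VK5211 vs placebo | b | 24-week risks | Difference (points) | Risk ratio |
|---|---|---|---|---|
| 50% vs 30% | 30% | 65.0% vs 51.0% | 20 to 14 | 1.67 to 1.27 |
| 50% vs 30% | 15% | 57.5% vs 40.5% | 20 to 17 | 1.67 to 1.42 |
| 35% vs 15% | 15% | 44.75% vs 27.75% | 20 to 17 | 2.33 to 1.61 |
| 4% vs 1% | 1% | 4.96% vs 1.99% | 3.00 to 2.97 | 4.0 to 2.5 |

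**4. The same quantities with a window of last dose + 28 days**
- Off-drug share for a completer: 28/112 = 25%.
- Rate ratio for R = 2, no carry-over: (2 × 84 + 28)/112 = 1.75. With 35 days of carry-over the effect covers all 112 days and the ratio is 2.00.
- First row of the table: the 28-day event-free probability is 0.70^(28/84) = 0.8879. Risks are 1 − 0.5 × 0.8879 = 55.6% and 1 − 0.7 × 0.8879 = 37.8%. The difference is 17.8 points and the risk ratio 1.47, between the 12-week values (20 points, 1.67) and the 24-week values (14 points, 1.27).

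**The case against.** Counting off-drug events is deliberate. Follow-up exists for safety and duration of effect, the objective speaks of overall adverse events, and an inclusive definition does not lose delayed harm. That stands: collection should not change and the all-study total should be kept. What is missing is the split.

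Drug effects may also outlast dosing. With about 30 days of carry-over the longer window largely repays its dilution. In an illustrative case (placebo 20% per 12 weeks, on-drug hazard ratio 2, 26 per arm), approximate power is 25% for a 12-week table, 15% for the open-ended table with no carry-over, and 22% with 30 days of carry-over. No AE test is planned, so these figures only show direction.

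A reader might infer more than the documents support:
- *That every TEAE table mixes the periods.* The shells are in a separate file (SAP 4.3), and a column or footnote there could show onset relative to dose. Only titles and text can be checked.
- *That real harms would be hidden.* Off-drug events are counted, AEs are listed by subject, a DMC sees unblinded data, and the excess in rare events barely moves.
- *That background risk off drug equals that on drug.* The introduction places peak mortality in the first three months after fracture. Dosing starts at 4 to 12 weeks, so follow-up starts at about week 16 to 24. For deaths at least, b is probably lower than the on-drug placebo risk and the dilution smaller.
- *That the SAP's Day 112 rule already separates AEs.* SAP 2.16 gives it for early-termination visit data. It equals last dose + 28 days only for someone dosed to Day 84; a subject who stops at Day 30 reaches that point at Day 58.

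**Conclusion.** The point holds as a gap in specification. The definition is open-ended in both documents, AE recording runs 12 weeks past the last planned dose, and nothing visible commits to an on-treatment comparison that matches the objective. About half of a completer's window is off drug (47% to 54% across visit windows).

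The consequence is conditional. Rate ratios move toward 1 if the effect lasts less than the full 84 off-drug days: in the assumed cases, 2 becomes 1.50 to 1.71 and 3 becomes 2.00 to 2.42 for carry-over of 0 to 35 days. Absolute differences fall noticeably only when off-drug background risk is high. The size rests on assumed AE rates, a constant background equal across arms, and an offset of effect that the documents show only for hormones. Because the comparisons are descriptive and onset dates allow an on-treatment table later, this is a cheap improvement to make before unblinding, not a threat to the trial's safety conclusions.

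**What to change.** In SAP 2.9.1 and Protocol 9.5.1:
- Define an on-treatment TEAE as onset or worsening from first dose through each subject's own last dose plus a stated lag.
- Justify the lag from the half-life (not given in these documents) and the offset of effect. Twenty-eight days is one option; the Phase I hormone data suggest effects may last up to about 35 days.
- Define later onsets as follow-up AEs.

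Present Tables 14.3.1.1.1 to 14.3.2.2.2 with on-treatment, follow-up and all-study columns. Make the on-treatment column the one that addresses the 12-week objective. Keep the all-study column so that delayed or withdrawal events are not lost. If the shells already contain such a split, state it in SAP 2.9.1.

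The cost is wording, extra columns and smaller counts per period. AE onset is already to be tabulated relative to dose, and the stringent DXA definition already needs each subject's treatment stop date, so no new data are required. A lag leaves some off-drug time in the window (25% for a completer at 28 days), so it reduces the dilution without removing it if the effect stops with dosing.

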2.9.2. Safety Laboratory Evaluations

Individual laboratory values will be listed by visit and summarized using descriptive statistics. Individual change from baseline in laboratory values will be calculated and summarized descriptively. Shift tables from baseline to final visit will also be produced for the laboratory

assessments based on the categories of Low, Normal, and High. Selected lab parameters will be summarized by CTC grade. A clinically significant change from baseline may be recorded as an AE if deemed appropriate by the PI or sponsor.

To better view the results of the liver function tests, the liver function tests will be presented in a separate table.

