7.7 Visit 4 (Day 84 -5/+2)

At Visit 4, the following will take place:

- Record concomitant medications
- Physical examination, including weight
- Vital signs (SBP, DBP, HR)
- Plasma concentration sample collection (pre-dose and 2 hours \pm 10 min post-dose)

- ECG at 2 hours post-dose
- Hematology/Chemistry/Urinalysis
- Thyroid Markers
- Vitamin D
- Bone Turnover Markers
- Pituitary/Adrenal Hormone Blood Tests
- Pancreatic Endocrine Markers
- Fasting Lipid Profile
- Coagulation
- PSA (males only)
- A light snack is permitted after bloodwork has been completed.
- DXA Scan
- Grip Strength and SPPB (to be performed before the PADLs/IADLs and SF-36)
- Post-fracture PADLs/IADLs
- SF-36
- 6MWT and BORG Scale(to be performed after the PADLs/IADLs and SF-36)
- Record adverse events
- Review diary card
- Review study treatment compliance and administer study treatment
- Schedule the Visit 5 DXA scan.

In case of early withdrawal, all Visit 4 events should be performed, excluding plasma drug concentration assessments and study drug dispensation.

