9.5.2 Laboratory Evaluations

Individual laboratory values will be listed by visit and summarized using descriptive statistics. Individual change from baseline in laboratory values will be calculated and summarized descriptively. Shift tables from baseline to final visit will also be produced for the laboratory assessments based on the categories of Low, Normal, and High. A clinically significant change from baseline may be recorded as an AE if deemed appropriate by the PI or sponsor.

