10.7 Clinical Findings

Any significant clinical findings will be followed until the condition returns to pre-study status, stabilized, or can be explained as not being IP related. This also applies to all AEs and SAEs that continue at the final visit. Any AE that occurred prior to the final visit will be followed up to 30 days after the final visit.

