2.1. General Statistical Methods

Efficacy analyses will be performed with both the Intent-to-Treat and Per Protocol Population. Safety analyses will be performed with the Safety Population. Data listings will be provided for all enrolled subjects.

All measured variables and derived parameters will be listed individually and, if appropriate, tabulated by descriptive statistics. For descriptive statistics, summary tables will include by treatment group summaries of sample size, arithmetic mean, standard deviation, coefficient of variation (if appropriate), median (and other percentiles, if appropriate), and minimum and maximum values. For categorical variables summary tables will include by treatment group summaries of frequency counts.

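### The liver shift table runs from baseline to an undefined final visit, so it uses at most one of three planned on-drug panels, and the text specifies no by-arm count of worst on-treatment ALT/AST

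*SAP*

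**What the plan says.** SAP 2.9.2 and Protocol 9.5.2 use the same rule. The SAP wording is "Shift tables from baseline to final visit will also be produced for the laboratory" "assessments based on the categories of Low, Normal, and High". The protocol wording is "Shift tables from baseline to final visit will also be produced for the laboratory assessments based on the categories of Low, Normal, and High". Neither section defines the final visit. SAP 2.16 assigns early-termination data to Month 3 or Month 6 by a Day 112 cut, but does not define the term either.

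The phrase appears elsewhere for the end of a subject's participation. Protocol 10.7 says "Any AE that occurred prior to the final visit will be followed up to 30 days after the final visit", and Protocol 2.8 (Visit 5) says "Subjects will exit the study". The last planned dose is at Visit 4, where Protocol 7.7 lists "Review study treatment compliance and administer study treatment".

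SAP 2.9.2 adds one graded display: "Selected lab parameters will be summarized by CTC grade". It does not name the parameters or say which value is graded. SAP 4.1 lists liver descriptive Table 14.3.3.1, liver shift Table 14.3.4.1 and CTC-grade shift Table 14.3.4.2. By SAP 4.3, the shells are in a separate file, which was not available for this review. For descriptive tables, SAP 2.1 provides by-arm statistics that include "median (and other percentiles, if appropriate), and minimum and maximum values".

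**The concern.** Comparing laboratory safety with placebo is a secondary objective, and there is a reason to look closely at transaminases. In the Phase I study in subjects aged 65 or older (Protocol Introduction), five subjects at 3 mg had raised AST or ALT: four mild, and one with ALT at 7 times the upper limit of normal (ULN) and AST just under 5 times. One subject at 1 mg had a minimal ALT rise. The 3 mg dose is above this trial's top dose, but 2 mg lies between the two and is given for 12 weeks.

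A shift to a single late sample records where a subject ended, not how high the value went on drug. A transient rise at Day 28 or Day 56 can disappear from it. If a reader of the study report takes the liver shift table as the summary of hepatic safety, it could look reassuring whatever happened during dosing.

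**Working it through.** The plan gives no figure to reproduce on this point. The check uses the visit schedule, the planned outputs and the Phase I values in the Protocol Introduction.

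1. **Liver panels after first dose, for a completer.** Table 1 and its footnote 13 schedule ALT, AST, GGT and total bilirubin at Visits 2, 3, 4 and 5, nominally Days 28, 56, 84 and 168. The last dose is at Visit 4, so 3 of the 4 are on drug.

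2. **Panels the shift table uses.** Final visit = Visit 4: 1 of 3 on-drug panels. Final visit = Visit 5: 0 of 3.

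3. **Time off drug at Visit 5.**
   - Visit 4 window: 84 − 5 = 79 to 84 + 2 = 86.
   - Visit 5 window: 168 − 5 = 163 to 168 + 5 = 173.
   - Gap: 163 − 86 = 77 days to 173 − 79 = 94 days; nominally 168 − 84 = 84.
   - If Visit 4 falls on Day 90, the limit in Protocol 2.7, the shortest gap is 163 − 90 = 73 days.

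4. **Which visit is meant.**
   - For Visit 5: Protocol 10.7 uses the term for the end of participation, subjects exit at Visit 5, and the liver tests are drawn there.
   - For Visit 4: the same sentence governs all laboratory shift tables, yet hematology and the rest of chemistry are not drawn at Visit 5. The safety objective refers to 12 weeks of treatment.
   - A last-available-value rule would give Visit 4 for most analytes and Visit 5 for the liver tests.

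   The documents do not settle it.

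5. **Width of the High category.** The Introduction gives an ALT limit of 55 U/L, assumed here to apply to the marked case too. The minimal case is 59/55 = 1.07 × ULN. The marked case is 7 × 55 = 385 U/L. Both fall in High, a range of 385/59 = 6.5-fold.

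6. **Could a marked rise read Normal at Visit 5?** This is an illustration only. The marked case fell from about 385 to 62 U/L (62/55 = 1.13 × ULN) in about 14 days. Assuming log-linear decline, the half-life is 14 / log2(385/62) = 5.3 days. A 7 × ULN peak at Visit 4 would be back at ULN within 77 days for any half-life up to 77 / log2(7) = 27 days. This rests on one subject, and the text does not say whether dosing had stopped.

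7. **What the other outputs add.**

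| Output | What it shows | What it leaves open |
|---|---|---|
| Table 14.3.3.1 | Arm maximum at each planned visit | Does not count subjects; SAP 2.16 ties descriptive statistics to planned visits |
| Listings (SAP 3.2) | Every value, sorted by treatment | No by-arm summary |
| AE tables with CTCAE grading | Rises reported as AEs, including from unscheduled tests | Under Protocol 10.2 an asymptomatic rise depends on follow-up action or judgment |
| Table 14.3.4.2 | Graded shifts for selected parameters | Parameters and graded value not stated |
| Monitoring committee (Protocol 10.1) | Unblinded safety review during the trial | Not a reported table |

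On the AE row, the Introduction itemizes the AEs in the 3 mg Phase I cohort, and the asymptomatic 7 × ULN rise is not among them. It appears only under laboratory evaluations.

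8. **A protocol commitment.** Protocol 9.5 promises the incidence of treatment-emergent abnormalities by dose. Neither SAP 2.9.2 nor any table title in SAP 4.1 names it.

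**The case against.** The strongest reply is that Visit 4 is probably what was meant. It is the one post-baseline visit that serves every listed shift table: if Visit 5 applied to all, the hematology shift table would be empty for completers. Visit 4 also fits the 12-week safety objective, and the early-termination visit is modeled on it. This stands as far as it goes. A reader might infer from Protocol 10.7 that the liver shift table is off drug by design, but the documents do not establish that. Protocol 10.7 concerns AE follow-up, not laboratory analysis. The point survives because the Visit 4 reading still leaves two of the three on-drug panels out of the table.

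The second reply is that the plan already covers the ground: a separate liver table with by-arm maxima, full listings, AEs graded by CTCAE and tabulated by maximum severity, early-termination data included under SAP 2.16, and an independent committee seeing unblinded safety data. Table 14.3.4.2 may grade ALT and AST at their worst, and the SAP does not revoke the Protocol 9.5 commitment. Most of this stands and limits the weight of the point. What remains is a count of subjects by arm and by height of rise that includes unscheduled tests and does not depend on someone having reported an AE.

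**Conclusion.** The point holds at modest weight. For a completer, the liver shift table uses one of three on-drug panels (Visit 4) or none (Visit 5, 77 to 94 days off drug by the Table 1 windows). On either reading, a rise that has reversed by the chosen sample is shown as Normal, and the Low/Normal/High scale does not separate a minimal rise from a marked one. The supplied text specifies no by-arm count of subjects by worst on-treatment ALT or AST.

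A reader might go further and conclude that the plan would hide a liver signal. The documents do not support that: on-drug values are collected, summarized by visit with maxima, and listed. The number of peaks missed cannot be estimated. The statement that no such count is specified applies to the SAP text and table titles; the shells, which were not available, might supply it. The decline illustration assumes log-linear recovery and a ULN of 55 U/L, and the conclusion does not depend on it. Efficacy is unaffected.

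**What to change.** In SAP 2.9.2:

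- Base Table 14.3.4.1, and the liver parameters of Table 14.3.4.2, on each subject's worst on-treatment value from all scheduled, unscheduled and early-termination samples.
- Define on-treatment as first dose to a stated number of days after last dose. SAP 2.10.2.1 uses 14 days for DXA. That is a possible starting point, but it was not chosen for liver tests and needs a clinical rationale.
- Count subjects by arm and by CTC grade or multiple of ULN (for example >1, >1.5, >3 and >5).
- Keep the baseline-to-final shift as a second panel, since Protocol 9.5.2 promises it, and define final visit there.
- Leave the planned-visit rule in SAP 2.16 unchanged.

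For the liver tests, this also supplies the incidence promised in Protocol 9.5.

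The cost is SAP wording and a defined input value for two tables already listed. It needs no new data and no protocol change. The downside is that unequal retesting can inflate worst values in one arm, so the number of unscheduled liver tests per arm should be shown beside the counts.
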